### 12.5.3. Reporting Standards for Pharmacokinetics

Pharmacokinetic Concentration Data	
PC Windows Non-Linear (WNL) File	PC WNL file (CSV format) for the non-compartmental analysis by Clinical Pharmacology Modelling and Simulation function will be created according to GUI_51487 . Note: Concentration values will be imputed as per GUI_51487
Descriptive Summary Statistics, Graphical Displays and Listings	Refer to IDSL PK Display Standards. Refer to IDSL Statistical Principle 6.06.1. Note: Concentration values will be imputed as per GUI_51487 for descriptive summary statistics/analysis and summarized graphical displays only.
NONMEM/Pop PK File	Pop-PK file (CSV format) for the POP-PK analysis by Clinical Pharmacology Modelling and Simulation function will be created according to the data specification detailed in the Data Analysis Plan (DAP) (GSK Document Number: 2018N381501_00 ).
Pharmacokinetic Parameter Derivation	
PK Parameter to be Derived by Programmer	All necessary PK parameters as defined in Section 9.1.5 (C max , t max , AUC(0-t), AUC(0-24), C τ ) will be derived by the Clinical Pharmacology Modelling and Simulation function.
Pharmacokinetic Parameter Data	
Is non-quantifiable (NQ) impacted PK Parameters Rule Being Followed	Yes, refer to Standards for Handling NQ Impacted PK Parameters.
Descriptive Summary Statistics, Graphical Displays and Listings	Refer to IDSL PK Display Standards.

**12.6. Appendix 6: Derived and Transformed Data**

**12.6.1. General**

Multiple Measurements at One Analysis Time Point

 
• Mean of the measurements will be calculated and used in any derivation of summary statistics but if listed, all data will be presented.
 
• If there are two values within a time window (as per Section 12.3.1) the earliest value in that window will be used.
 
• Participants having both High and Low values for Normal Ranges at any post-baseline visit for safety parameters will be counted in both the High and Low categories of “Any visit post-baseline” row of related summary tables. This will also be applicable to relevant Potential Clinical Importance summary tables.
 

Study Day

 
• Calculated as the number of days from First Dose Date:             
 
• Ref Date = Missing → Study Day = Missing
 
• Ref Date < First Dose Date → Study Day = Ref Date – First Dose Date
 
• Ref Date ≥ First Dose Date → Study Day = Ref Date – (First Dose Date) + 1
 
 
 

**12.6.2. Study Population**

Extent of Exposure

 
• Number of days of exposure to study drug will be calculated based on the formula: Duration of Exposure in Days = Treatment Stop Date – (Treatment Start Date) + 1
 
• Participants who were randomized but did not report a treatment start date will be categorised as having zero days of exposure.
 
• If there are any treatment breaks during the study, exposure data will be adjusted accordingly.
 

Demographics

 
• Body mass index (BMI) will be calculated as: Weight (kg) at screening / [Height (m)]
 

**12.6.3. Efficacy**

Efficacy
CFU

 
• Baseline CFU will be calculated as: Mean (log10(CFU Day -1), log10(CFU Day -2))
 
• Log(CFU) will be calculated as: Log(CFU/ml) = log10(mean(Total count 1:Total Count 2)*2*5*10^Dilution)
 

Efficacy

where:
 
 
• Total count 1 and total count 2 are the bacterial counts from plates 1 and 2 respectively. Where plate counts are reported as Too Numerous To Count (TNTC), a value of 2500 will be imputed. If a count is only available for 1 plate, then that count will be used instead of the mean.
 
• Dilution is the dilution factor for that plate.
 
• In the calculation, the *2 represents the 1:1 dilution of the original specimen and the *5 represents the 0.2 ml (200 µl) inoculation of the specimen.
 
• For bacteria counts with a comment of "Half of plate X was contaminated so only half the plate was counted", the count for that plate will be doubled for the analysis.
 

TTP

 
• The mean of the time to positivity for both plates (plate 1 and plate 2) at each timepoint will be calculated and used in any derivation of summary statistics and analyses. If a result is only available for 1 plate, then that value will be used instead of the mean. Where listed, all data will be presented.
 

#### 12.6.4. Safety

Laboratory Parameters

 
• If a laboratory value which is expected to have a numeric value for summary purposes, has a non-detectable level reported in the database, where the numeric value is missing, but typically a character value starting with '<x' or '>x' (or indicated as less than or greater than x in the comment field) is present, the number of decimal places in the observed values will be used to determine how much to add or subtract in order to impute the corresponding numeric value. 
 
• Example 1: 2 decimal places = '< x' becomes <math>x - 0.01</math>
 
• Example 2: 1 decimal place = '> x' becomes <math>x + 0.1</math>
 
• Example 3: 0 decimal places = '< x' becomes <math>x - 1</math>
 
 
 
• For values '<=x' or '>=x' the value itself ('x') should be imputed as the numeric value.
 

 
• Mean arterial blood pressure (BP) will be calculated as:  Mean arterial BP (mmHg) = <math>1/3</math> (systolic BP (mmHg)) + <math>2/3</math> (diastolic BP (mmHg))
 

#### 12.6.5. Pharmacokinetic

Pharmacokinetic Parameters
Derived Pharmacokinetic Parameters

 
• Pharmacokinetic parameters will be calculated by standard non-compartmental analysis according to current working practices and using the currently supported version of WinNonlin 5.2 or higher.
 
• All calculations of non-compartmental parameters will be based on actual sampling times recorded during the study.
 

**Pharmacokinetic Parameters**

- The following pharmacokinetic parameters will be determined and summarised, as data permit.:

Parameter	Parameter Description
AUC(0-t)	Area under the concentration-time curve from time of dosing to last quantified concentration, regardless of time.
AUC(0-24)	Area under the concentration-time curve from time of dosing extrapolated to 24 hours
C max	Maximum observed plasma drug concentration, determined directly from the concentration-time data.
t max	Time to reach C max , determined directly from the plasma drug concentration-time data
C τ	Trough concentration

- Additional parameters may be calculated.
- All calculated parameters will be listed.
- For graphical displays, IDSL Statistical Principles 7.01 to 7.13 and the standards for the transfer and reporting of PK data using HARP will be followed.

## 12.7. Appendix 7: Reporting Standards for Missing Data

### 12.7.1. Premature Withdrawals

Element	Reporting Detail
General	
 
Participant study completion is defined as a participant who has completed all phases of the study including the last visit (the follow-up visit).
 
Withdrawn participants may be replaced in the study.
 
All available data from participants who were withdrawn from the study will be listed and all available planned data will be included in summary tables and figures, unless otherwise specified.
 
Withdrawal visits will be slotted as per Appendix 3: Assessment Windows or will be summarised as withdrawal visits.
 

### 12.7.2. Handling of Missing Data

Element	Reporting Detail
General	
 
Missing data occurs when any requested data is not provided, leading to blank fields on the collection instrument: 
 
These data will be indicated by the use of a “blank” in participant listing displays. Unless all data for a specific visit are missing in which case the data are excluded from the listing.
 
Answers such as “Not applicable” and “Not evaluable” are not considered to be missing data and should be displayed as such.
 
 
 

Outliers	
 
Any participants excluded from the summaries and/or statistical analyses will be documented along with the reason for exclusion in the clinical study report.
 

#### 12.7.2.1. Handling of Missing and Partial Dates

Element	Reporting Detail
General	
 
Partial dates will be displayed as captured in participant listing displays.
 

Adverse Events	
 
The eCRF allows for the possibility of partial dates (i.e., only month and year) to be recorded for AE start and end dates; that is, the day of the month may be missing. In such a case, the following conventions will be applied for calculating the time to onset and the duration of the event: 
 
Missing Start Day: First of the month will be used unless this is before the start date of study treatment; in this case the study treatment start date will be used and hence the event is considered On-treatment as per Appendix 4: Study Phases and Treatment Emergent Adverse Events.
 
Missing Stop Day: Last day of the month will be used, unless this is after the stop date of study treatment; in this case the study
 
 
 

Element	Reporting Detail
	
treatment stop date will be used.
 
 
• Completely missing start or end dates will remain missing, with no imputation applied. Consequently, time to onset and duration of such events will be missing.
 
• AEs with entirely missing or unknown start dates will be assumed to be on-treatment for reporting.
 
• AEs with missing end dates are not anticipated to affect reporting.
 
• AEs with missing start or end times which started on the same day as study treatment or ended on the same day as study treatment plus 2 days will be assumed to be on-treatment for reporting and classed as treatment emergent for adverse events.
 

Concomitant Medications/ Medical History
	
 
• Partial dates for any concomitant medications recorded in the eCRF will be imputed using the following convention: 
 
○ If the partial date is a start date, a '01' will be used for the day and 'Jan' will be used for the month
 
○ If the partial date is a stop date, a '28/29/30/31' will be used for the day (dependent on the month and year) and 'Dec' will be used for the month.
 
 
 

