**5.4. Participant and Study Completion**

A participant is considered to have completed the study if he/she has completed all phases of the study including the last visit (the ‘follow-up’ visit). A participant is considered to have completed the study treatment phase once they have received the final dose of study treatment on Day 14.

The end of the study is defined as the date of the last visit of the last participant in the study.

Following completion of the study treatment phase and after discharge from hospital the participants will be provided with their first dose/s of standard TB therapy (i.e. Rifafour

e-275 or equivalent generic alternative) with appropriate counselling. All participants will be referred to the local community TB clinics to receive the remainder of a full course of standard antituberculosis chemotherapy according to national guidelines. The participants will be provided with a referral letter to take with them to the TB clinic. Within a week of the participant's discharge from the study clinic, a follow-up call will be made by the study site staff to the TB clinic to determine if the participant attended the clinic.

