### 9.2.1. Time Period and Frequency for Collecting AE and SAE Information

- All SAEs will be collected from the start of treatment until the follow-up visit at the time points specified in the SoA (Section 2). However, any SAEs assessed as related to study participation (e.g., study treatment, protocol-mandated procedures, invasive tests, or change in existing therapy) or related to a GSK product will be recorded from the time a participant consents to participate in the study.
- All AEs will be collected from the start of treatment until the follow-up visit at the time points specified in the SoA (Section 2).
- Medical occurrences that begin before the start of study treatment but after obtaining informed consent will be recorded on the Medical History/Current Medical Conditions section of the case report form (CRF) not the AE section.
- All SAEs will be recorded and reported to the Sponsor or designee immediately and under no circumstance must this exceed 24 hours, as indicated in [Appendix 5](#). The Investigator will submit any updated SAE data to the Sponsor within 24 hours of it being available.
- Investigators are not obligated to actively seek AEs or SAEs in former study participants. However, if the Investigator learns of any SAE, including a death, at any time after a participant has been discharged from the study, and he/she considers the event to be reasonably related to the study treatment or study participation, the Investigator must promptly notify the Sponsor.
- The method of recording, evaluating, and assessing causality of AEs and SAEs and the procedures for completing and transmitting SAE reports are provided in [Appendix 5](#).

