- l. Overnight sputum sampling may start at Screening visit (day -9 to -3) or on Visit 2 (day -2) and will continue daily until Visit 7 (day 4). Additional sampling will be conducted at visit 9 (day 6), Visit 11 (day 8), Visit 13 (day 10), Visit

15 (day 12) and Visit 17 (day 14). Sputum sampling will stop on the morning of Visit 18 (day 15). Sputum collection will start in the afternoons at 15:00 hours ( $\pm 1$  hour) and continue for 16 hours overnight. The 16-hour sputum sampling for each of the sampling days must be finished prior to the administration of the next day's IP. Overnight sputum collection may be collected as many times as required over the screening period until an eligible sample is obtained. Of the pre-treatment period samples collected, only the Visit 2 (day-2) and Visit 3 (day -1) overnight sputum samples will be used for the efficacy endpoint tests.

The day sputum collection starts reflects the day to which that sample applies. e.g. a sample whose collection starts on day 1 and ends on day 2, is designated as the day 1 overnight sputum sample (and results).

- m. Randomization may occur once all the screening results are available and the Investigator has determined that the participant is eligible for the trial.
- n. After the first dose of IP, subsequent doses of IP will be administered 23 to 25 hours after the previous dose.
- o. Minimum inhibitory concentration (MIC) and speciation of the infecting organism by polymerase chain reaction (PCR) will be estimated from a culture collected on a pre-treatment day (day-1 or day-2) and from the last available culture on a treatment day (day 14 or earlier, but not earlier than day 8). Drug susceptibility testing of *M. tuberculosis* for sensitivity to rifampicin with a molecular method will be tested at Visit 1. Susceptibility to INH, Rif, EMB and PZA will be tested on a culture grown from a baseline sample (day -2 or day -1). The analysis of any bacterial isolates sent to GSK, Spain for further characterisation in the event of MIC change will not be reported in the clinical study report and will be reported separately.
- p. Adverse events (AE) will be collected by the Investigator from the time a participant receives his/her first dose of IP through to the Visit 19 (day 28) Follow up Visit.
- q. CC
- r. [not used]

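### The cap on partial AE stop dates puts the stop before the start when an AE begins after the last dose and only its stop day is missing

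*SAP*

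**What the plan says.** SAP 12.7.2.1 foresees incomplete AE dates: "The eCRF allows for the possibility of partial dates (i.e., only month and year) to be recorded for AE start and end dates". It then states what the imputed dates are for: "the following conventions will be applied for calculating the time to onset and the duration of the event".

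- **Missing stop day:** "Last day of the month will be used, unless this is after the stop date of study treatment"; in that case the study "treatment stop date will be used".
- **Missing start day:** "First of the month will be used unless this is before the start date of study treatment", in which case the treatment start date is taken.
- **Completely missing start or end date:** left missing.

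The stop-day rule does not require the imputed stop to fall on or after the AE start. It makes no exception for AEs that begin after treatment.

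On collection, Protocol 9.2.1 says "All AEs will be collected from the start of treatment until the follow-up visit at the time points specified in the SoA". SAP 12.2.1 gives the period as "from the time a participant receives his/her first dose of IP through to the Visit 19 (day 28) Follow up Visit", and that visit has a window of 7 days either side. Under Protocol 5.4 the treatment phase is complete once the participant has "received the final dose of study treatment on Day 14". SAP 12.4.1 defines a post-treatment AE phase that begins 48 hours after treatment stop.

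**The concern.** The cap treats the treatment stop date as the latest plausible end of any AE with a partial stop date. In this study AE collection runs on for a nominal two weeks after the last dose, and the SAP has a phase category for events that arise then. The cap even falls before the end of the SAP's own treatment-emergent window, which is treatment stop plus 48 hours (SAP 12.4.2).

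Two kinds of AE are mishandled. One that begins after the last dose can be given an impossible duration. One that begins on treatment and outlasts it is recorded as ending with the last dose. Wherever derived duration is used, such AEs would look shorter than they were, or would carry a value that cannot be true.

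**Working it through.** The plan states no figure to reproduce, so the check applies the rule as written.

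**Inputs**
- Day 1 is the first dose, and Day 14 is the last dose for a completer (Protocol 5.4).
- AEs are collected to Day 28, window Day 21 to Day 35 (schedule of activities; SAP 12.3.1).
- Imputed stop = month end if that is on or before treatment stop; otherwise treatment stop.
- Imputed start = the later of the first of the month and treatment start.
- Duration: the SAP gives no AE formula. Stop - start + 1 is assumed here, by analogy with the exposure formula in SAP 12.6.2.

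**Why the inversion is certain when the start is known.** Suppose the AE starts after treatment stop. The recorded stop month cannot end before the AE starts, so it ends after treatment stop. The cap therefore applies, and the imputed stop (treatment stop) is earlier than the start. This does not depend on the calendar.

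**Worked examples.** Take a first dose on 1 June, so Day *n* is *n* June and the last dose is 14 June.
- Start 20 June, stop recorded as June: month end 30 June is after 14 June, so the stop becomes 14 June. Duration = 14 - 20 + 1 = -5 days (14 - 20 = -6 without the +1).
- Start 12 June, true stop 26 June, recorded as June: the stop becomes 14 June. Duration = 14 - 12 + 1 = 3 days; the true value is 26 - 12 + 1 = 15.

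**Enumeration.** All 365 first-dose dates of an illustrative year (2021, an assumption) were combined with every onset and stop day up to Day 28. All pairs are weighted equally, so the counts show how the rule behaves and are not expected frequencies.

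| Situation | Day pairs × dates | Result |
|---|---|---|
| Onset Days 15-28, start known, stop day missing | 105 × 365 = 38,325 | stop before start in 38,325; stop minus start from -1 to -14 days |
| Onset Days 1-14, true stop Days 15-28, stop day missing | 14 × 14 × 365 = 71,540 | no inversion, but stop too early in 71,540 |
| Onset Days 15-28, start and stop days both missing | 38,325 | stop before start in 6,720 (6,720 / 38,325 = 17.5%) |

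With the +1 convention, a Day 15 onset gives 14 - 15 + 1 = 0 days rather than a negative number; the stop still precedes the start.

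In the last row, inversion needs the start month to begin after treatment stop. For example, with first dose 10 June and last dose 23 June (10 + 13), an AE recorded only as July gets start 1 July and stop 23 June. Otherwise the start is moved back into the treatment period and no inversion shows.

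**Check of the remedy.** Use the earlier of the month end and Day 28 (taken as last contact), never before the AE start: 0 of 38,325 combinations invert. In the June examples the stop becomes 28 June. Durations are then 28 - 20 + 1 = 9 days and 28 - 12 + 1 = 17 days. The second overstates the true 15 by 2 days but is a possible value.

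**The case against.** The strongest case against is about reach, and most of it stands.

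- **No planned table is shown to be affected.** The AE tables in SAP 12.10.7 report subjects, occurrences, maximum grade or exposure-adjusted rates; none is titled as a duration summary. Study phase and the treatment-emergent flag (SAP 12.4.1, 12.4.2) and the pandemic split (12.4.1.2) rest on onset. Listings show partial dates as captured. A derived duration might appear in the AE listings, but their standard shell is not in the documents. A reader might infer that AE incidence or treatment-emergent counts are corrupted; the documents do not support that.
- **The trigger is narrow.** It needs a stop month and year without a day. Participants stay in hospital until discharge on Day 15, so missing days should be uncommon up to then. Exposure is mainly from AEs that resolve between discharge and the follow-up visit. A reader might infer that every AE arising in follow-up inverts. That is not so: complete stop dates are unaffected, wholly missing ones stay missing, and with the start day also missing only some invert.
- **The SAP expects little effect.** SAP 12.7.2.1 remarks that missing AE end dates should not affect reporting. That fits a low severity but does not withdraw the stop-day rule, which still assigns a value for calculating duration.

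Two further inferences are tempting. One is that about half the AE data are at risk, because follow-up is 14 of 28 nominal days. That is a share of calendar time, ranging from 7/21 (33%) to 21/35 (60%) across the visit window, and says nothing about how many AEs have partial stop dates. The other is that the long half-life makes reactions outlast dosing. Protocol 5.6 gives 45 hours, while Appendix 6 equates five half-lives with 6 days (6 × 24 / 5 = 28.8 hours). Neither document links AE duration to half-life, and the point does not need it.

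Nothing in either document limits the rule to on-treatment AEs or prevents the inversion. The same SAP table imputes partial medication stop dates without any treatment-stop cap.

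**Conclusion.** The rule is wrong as written, with small consequences. For an AE with a known start after the last dose and only the stop day missing, the imputed stop always precedes the start, by 1 to 14 days for onsets on Days 15 to 28. For an AE that begins on treatment and resolves after the last dose with the stop day missing, duration is always understated. With both days missing, only some AEs invert.

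The effect is limited to derived AE duration for partial stop dates. No effect on efficacy results, AE incidence tables or onset-based classification is shown, so severity is low. The number of AEs affected cannot be estimated from the documents.

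The day counts assume a last dose on Day 14 and, where durations are quoted, the stop - start + 1 formula. An earlier treatment stop moves the cap earlier and widens the affected period. Dropping the +1 reduces each duration by one day and changes no conclusion.

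**What to change.** In SAP 12.7.2.1, replace the cap for a missing AE stop day. Impute the earlier of the last day of the recorded month and the date of the participant's last study contact (follow-up or early withdrawal visit), and never a date before the AE start date. Where the start day is also missing, apply the last condition to the imputed start. In the same place, state the AE duration formula, since none is given.

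The cost is a sentence or two in the SAP and a small change to the date-derivation program. No data collection, clinical rule or planned display has to change.

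The imputed stop will sometimes be later than the true one, as in the 17-day against 15-day example, but it can no longer precede the start.

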## 12.8. Appendix 8: Values of Potential Clinical Importance

### 12.8.1. Laboratory Values

Haematology				
Laboratory Parameter	Units	Category	Clinical Concern Range	
			Low Flag (< x)	High Flag (>x)
Hematocrit	Ratio of 1	Male		0.54
		Female		0.54
		Change from Baseline	Decrease of 0.075	
Haemoglobin	g/L	Male	75	180
		Female	75	180
		Change from Baseline	Decrease of 25	
Lymphocytes	x10  / L		0.8	
Neutrophil Count	x10  / L		0.5	
Platelet Count	x10  / L		100	550
While Blood Cell Count (WBC)	x10  / L		3	20

Clinical Chemistry				
Laboratory Parameter	Units	Category	Clinical Concern Range	
			Low Flag (< x)	High Flag (>x)
Albumin	g/L		20	
Calcium	mmol/L		2	2.75
Creatinine	%	Change from Baseline		Increase of 30%
Glucose	mmol/L		3	11
Potassium	mmol/L		3	5.5
Sodium	mmol/L		130	150

Liver Function				
Test Analyte	Units	Category	Clinical Concern Range	
ALT / SGPT	IU/L	High	≥ 3x ULN	
AST / SGOT	IU/L	High	≥ 3x ULN	
AlkPhos	IU/L	High	≥ 2x ULN	
T Bilirubin	µmol/L	High	≥ 1.5x ULN	
T. Bilirubin + ALT	µmol/L	High	1.5x ULN T. Bilirubin	

Liver Function			
Test Analyte	Units	Category	Clinical Concern Range
			+
	U/L		≥ 2x ULN ALT

ULN = Upper Limit of Normal; ALT=Alanine Aminotransferase; AST=Aspartate Aminotransferase; SGPT=Serum Glutamic Pyruvic Transaminase; SGOT=Serum Glutamic Oxaloacetic Transaminase; T. Bilirubin=Total Bilirubin

